**7.0 SUPPORTIVE CARE AND OTHER CONCOMITANT THERAPY**

**7.1 Concurrent Anticancer Therapy**

Concurrent cancer therapy, including chemotherapy, radiation therapy, immunotherapy, or biologic therapy may NOT be administered to patients receiving study drug. If these treatments are administered the patient will be removed from protocol therapy.

**7.2 Investigational Agents**

No other investigational agents may be given while the patient is on study.

**7.3 Supportive Care**

Appropriate antibiotics, blood products, antiemetics, fluids, electrolytes and general supportive care are to be used as necessary. Specific supportive care measures for

management of autoimmune reactions are detailed below:

#### Skin Related Toxicity

For skin-related Grade 3 autoimmune toxicity lasting > 7 days or Grade 4 autoimmune toxicity, including severe generalized pruritis or rash, symptomatic treatment will be given and patients will be removed from protocol therapy. Therapy will be as clinically indicated and may include local skin care, antihistamines, or corticosteroids (which can be local/topical or systemic). The use of topical corticosteroids for grades 1 -3 dermatitis will be allowed, and will not require patients to be removed from study. In the case of late-occurring hypersensitivity symptoms (e.g., appearance within one week after treatment of a localized or generalized pruritis), symptomatic treatment may be given (e.g., oral antihistamine, topical steroids for the skin). A dermatologist should evaluate persistent (lasting >7 days) and/or severe rashes or pruritus. A biopsy should be performed if appropriate and photos should be obtained.

#### Ocular Toxicity

Patients who report any new visual symptom, ocular findings on exam, or change in vision should be immediately referred to an ophthalmologist. Ophthalmologic evaluation should include but will not be limited to examination of the conjunctiva, anterior and posterior chambers and retina, normal and dilated slit-lamp examination. The patient will be treated as deemed appropriate by the ophthalmologist, including peri-ocular steroid injections or steroid eye drops if necessary.

#### Gastrointestinal Toxicity

Any patient experiencing diarrhea (which may be defined as watery stool, or increase in the frequency stools above grade 1 with urgency or nocturnal bowel movement, or melena or hematochezia) should be further evaluated for etiology that should include a search for an infectious etiology, *C. Difficile* colitis and other alternative infections as clinically indicated. Consideration should be given to discontinuing medications known to exacerbate colitis. Grade 2 or greater diarrhea attributable to protocol therapy is considered a DLT as outlined in [Section 5.4.1](#).

It is recommended that colitis or enterocolitis of Grade 1 be evaluated as above for other non-immune mediated causes, then monitored closely and treated symptomatically without steroids, including a trial of loperamide may be used. For Grade  $\geq 2$  colitis or enterocolitis, recommendations include endoscopy. Even if colonoscopy does not reveal gross findings of colitis, biopsies should be performed and strong consideration should be given to upper endoscopy and biopsies. Patients with gross or biopsy proven colitis or enteritis should receive IV steroids (recommend 1 mg/kg methylprednisone daily x 7 days) followed by a minimum 30 day taper. In patients with Grade 3 or 4 enterocolitis that does not respond to high dose steroids after 7 days, further therapies should be administered as clinically indicated in consultation with gastroenterology subspecialists.

Concern for immune-mediated liver toxicity may be elicited following LFT elevation of 3 fold over baseline and/or right upper quadrant abdominal pain or unexplained nausea or vomiting. Other etiologies for transaminitis should be considered and evaluated and may include but are not limited to neoplastic, concurrent medications, viral hepatitis, and other toxic etiologies. Evaluation for autoimmune etiologies may be evaluated by ANA, pANC, and anti-smooth muscle antibody tests as well as hepatology consultation with possible biopsy.

Pancreatitis has rarely been associated with checkpoint inhibitors and should be considered in cases of abdominal pain associated with elevations of amylase and lipase. Treatment of pancreatitis should be supportive and may include consultation with gastroenterology subspecialists.

#### Endocrine Toxicity

Patients experiencing symptoms such as fatigue, myalgias, impotence, mental status changes, constipation, or other symptoms thought to be associated with endocrine abnormalities should be evaluated for thyroid, pituitary, or adrenal endocrinopathies and an endocrinologist should be consulted.

Patients with Grade 2 hypothyroidism should be evaluated by an endocrinologist for further management. Patients with Grade 2 hypothyroidism or Grade 2 hyperthyroidism adequately managed with thyroid hormone replacement or thyroid suppression may continue on protocol therapy. Patients with Grade 3 or greater hypothyroidism will be considered to have had a dose-limiting toxicity. These patients should be managed according to [Section 6.11](#) and evaluation by an endocrinologist is recommended for further management. Patients who enter the study on thyroid replacement or suppression should have their thyroid medication adjusted to maintain TSH in the normal range.

#### Auto Immune or Immune System Disorders Effecting Other Organ Systems

Patients experiencing symptoms that may be associated with autoimmune or immune mediated adverse events possibly, probably or definitely related to protocol therapy should be evaluated and monitored closely. These may include but are not limited to pneumonitis, sarcoid-like granuloma and neurologic events including hypophysitis, encephalitis, aseptic meningitis, and cranial neuropathy especially nVII. Consideration should be given to subspecialty consultation particularly if systemic immune suppression is considered.

#### 7.4 **Growth Factors**

Growth factors that support platelet or white cell number or function can only be administered for culture proven bacteremia or invasive fungal infection. Patients MUST NOT receive prophylactic myeloid growth factor in the first cycle of therapy. The Study Chair should be notified before growth factors are initiated.

## 8.0 EVALUATIONS/MATERIAL AND DATA TO BE ACCESSIONED

### 8.1 Required Clinical, Laboratory and Disease Evaluation

All clinical and laboratory studies to determine eligibility must be performed within 7 days prior to enrollment unless otherwise indicated. Laboratory values used to assess eligibility (see [Section 4.0](#)) must be no older than seven (7) days at the start of therapy. Laboratory tests need **not** be repeated if therapy starts **within** seven (7) days of obtaining labs to assess eligibility. If a post-enrollment lab value is outside the limits of eligibility, or laboratory values are older than 7 days, then the following laboratory evaluations must be re-checked within 48 hours prior to initiating therapy: CBC with differential, bilirubin, ALT (SGPT) and serum creatinine. If the recheck is outside the limits of eligibility, the patient may not receive protocol therapy and will be considered off protocol therapy. Imaging studies must be obtained within 14 days prior to start of protocol therapy (repeat the tumor imaging if necessary).

STUDIES TO BE OBTAINED	Pre-Study	During Cycle 1	Prior to Subsequent Cycles ^
History	X	Weekly	X
Physical Exam with vital signs	X	Weekly	X
Height, weight, BSA	X		X
Performance Status	X		X
Pregnancy Test 	X		
CBC, differential, platelets	X	Weekly 	Weekly 
Urinalysis	X		X
Electrolytes including Ca ++ , Cl, PO 4 , Mg ++	X	Weekly	X
Creatinine, ALT*, AST*, bilirubin	X	Weekly	X
Amylase, lipase, CRP	X		X
TSH 	X	End of Cycle 1	X
Tumor Disease Evaluation- Parts A and B	X	End of Cycle 1	End of cycle 2, then q 3 cycles 
Tumor Disease Evaluation- Parts C, D, and E	X	End of Cycle 2	End of cycle 4, then q 3 cycles 
Pulse Oximetry	X		With Tumor Disease Evaluation
Pharmacokinetics  (Required)	X	X 	X
Vaccine Antibody and Cytokine Studies  (Optional)	X	X	X
Anti-Drug Antibody (ADA)  (Required)	X	X	X
Tumor Tissue (Required, if available)	X 		X 
EKG  , ECHO 	X	Clinically Indicated	
CPK and Troponin 	X	Clinically Indicated	

^ Studies may be obtained within 72 hours prior to the start of the subsequent cycle.

\* For the purpose of this study, the ULN for SGOT (AST) is 50 U/L and the ULN for SGPT (ALT) is 45 U/L.

 Women of childbearing potential require a negative pregnancy test prior to starting treatment. Men and women must be willing to adhere to effective contraception during the study and for 5 months after the last dose of nivolumab for women of childbearing potential and 7 months after the last dose of nivolumab for men sexually active with women of childbearing potential. Abstinence is an acceptable method of birth control.

 If patients have Grade 4 neutropenia then CBCs should be checked at least every other day until recovery to Grade 3 or until meeting the criteria for dose limiting toxicity.

- 3 If patients develop Grade 4 neutropenia then CBCs should be checked every 3 to 4 days until recovery to Grade 3
- 4 Free T4 should also be measured for patients with an abnormal TSH level. Guidance on the management of patients who develop hypothyroidism is included in [Section 7.3.4](#).
- 5 Tumor Disease Evaluation should be obtained on the next consecutive cycle after initial documentation of either a PR or CR. Please note that if the institutional investigator determines that the patient has progressed based on clinical or laboratory evidence, he/she may opt not to confirm this finding radiographically. If tumor growth is > 20% but < 40%, imaging to include target lesions must occur every cycle if clinically indicated, or if “pseudoprogression” appears based on inflammatory response, and the same radiographic and clinical criteria must be met in order to remain on study (See [Section 12.2.1](#)).
- 6 See [Section 8.3.2](#) and [Appendix III](#) for timing of PK studies.
- 7 Patients who are removed from therapy during Cycle 1 after receiving the dose of nivolumab on Day 15 should have their last PK sample collected on Day 28 of Cycle 1.
- 8 See [Section 8.4.2](#) and [Appendix IV](#) for timing of vaccine antibody and section [8.8.2](#) and [Appendix VII](#) for timing of cytokine studies.
- 9 See [Section 8.5.2](#) and [Appendix V](#) for timing of ADA studies.
- 10 See [Section 8.6](#) and [Appendix VI](#) for instructions for submitting tumor specimens. If tissue blocks or slides are unavailable, the study chair must be notified prior to study enrollment.
- 11 In the event a subject requires a biopsy for surgery and tumor tissue is removed, tissue will be requested for PD-L1 and CD8 Expression analysis (required, if available).
- 12 12-lead EKG and ECHO to be obtained at baseline, in patients with a history of CHF or at risk because of underlying cardiovascular disease or exposure to cardiotoxic drugs Refer to [section 4.2.7](#)
- 13 For patients with evidence of myocardial infarction (MI), cardiomyopathy, myositis, congestive heart failure (CHF) while on study, cardiac evaluations should be performed including lab tests, cardiology consultations as clinically indicated, including EKG, CPK, troponin, ECHO cardiogram. A CK-MB test may be used as a follow-up test to an elevated CK in order to determine whether the increase is due to heart damage or skeletal muscle damage. Refer to [section 6.1.4](#), [5.4.1](#)

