#### 5.1.5 Part E

The combination of nivolumab 1 mg/kg and ipilimumab 3 mg/kg will be administered every 3 weeks X 4 followed by nivolumab 3 mg/kg administered every 2 weeks until off protocol criteria in Section 10.1 are met. Note that cycle length is 21 days for the first 4 cycles of Part E; in cycle 5 and for subsequent cycles, cycle length will be 28 days and nivolumab 3 mg/kg will be administered

on days 1 and 15 of each cycle.

Dose Level	Cycles 1-4 (21-day Cycles)	Cycles 5+ (28-day Cycles)
1	Nivolumab (IV over 30 min) 1 mg/kg on Day 1  Ipilimumab (IV over 90 min) 3 mg/kg on Day 1	Nivolumab (IV over 30 min) 3 mg/kg on Days 1 and 15

Infusion of ipilimumab (over 90 minutes) should be initiated no sooner than 30 minutes after completion of the nivolumab infusion. If nivolumab therapy is withheld, ipilimumab should also be withheld.

Vital signs (temperature, pulse, blood pressure and respirations) will be monitored closely baseline then every 15 minutes x 2, then every 30 minutes x 3 beginning at the initiation of administration of ipilimumab infusion. Patients who develop symptoms or signs of hypotension ( $\geq 25\%$  decrease in systolic or diastolic blood pressures from baseline) that are temporally related to ipilimumab infusion will receive additional IV fluids as appropriate until the signs and symptoms resolve. During cycle 1, patients must remain for observation for a total of 6 hours following completion of ipilimumab. The post administration observation period may be extended to 24 hours and the patient admitted if clinically indicated. If the patient tolerates the first infusion of ipilimumab without incident, the observation period may be reduced to 90 minutes following completion of the drug infusion with subsequent cycles. Any patient who develops Grade 3 or 4 anaphylaxis felt to be primarily related to administration of ipilimumab will be removed from protocol therapy.

5.2 **Protocol therapy will continue to be administered until patient meets one of the off protocol criteria in [Section 10.1](#). Criteria for Starting Subsequent Cycles**

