A cycle may be repeated every 28 days for Parts A and B (and either every 21 days or 28 days for Parts C, D, and E) if the patient has again met the parameters as defined in the eligibility section, [Section 4.0](#), has not met any of the criteria for removal from therapy per [Section 10.1](#), and has not experienced a dose-limiting toxicity. A delay of up to 7 days from the date of the next scheduled treatment dose may be allowed. Please note the following exceptions:

- Patients may continue on to the next cycle if Pancreatic Function is  $\leq$  Grade 1 (See [Section 6.5](#))
- Patients who experience pleural effusion may continue onto the next cycle upon resolution as per [Section 6.8](#).

5.3 **Grading of Adverse Events**

Adverse events (toxicities) will be graded according to the NCI Common Terminology Criteria for Adverse Events (CTCAE) version 5.0. All appropriate treatment areas should have access to a copy of the CTCAE version 5.0. A copy of the CTCAE version 5.0 can be downloaded from the CTEP web site [http://ctep.cancer.gov/protocolDevelopment/electronic\\_applications/ctc.htm](http://ctep.cancer.gov/protocolDevelopment/electronic_applications/ctc.htm). Any suspected or confirmed dose-limiting toxicity should be reported immediately (within 24 hours) to the Study Chair.

5.4 **Definition of Dose-Limiting Toxicity (DLT)**

DLT will be defined as any of the following events that are possibly, probably, or definitely attributable to protocol therapy. DLT definitions will be the same for all parts. The DLT

observation period for the purposes of dose-escalation in Part C or dose de-escalation in Part A will be the first cycle of therapy. Toxicities with subsequent cycles will be monitored carefully and if significant numbers of delayed toxicities are observed, consideration will be given to a protocol amendment to focus on delayed toxicities in assessing the MTD.

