#### 5.4.1 Non-Hematological DLT:

- Any Grade 3 or Grade 4 non-hematological toxicity attributable to protocol therapy with the specific exclusion of:
  - a. Grade 3 ALT that returns to levels that meet initial eligibility criteria or baseline within 7 days and does not require systemic immunosuppression. **Note:** For the purposes of this study the ULN for ALT is defined as 45 U/L. Adverse event grades will be based on increases above the upper limit of normal, regardless of the subject's baseline. See [Appendix IX](#) for toxicity grading table.
  - b. Grade 3 liver enzyme elevation, including AST/SGT that returns to baseline within 7 days and does not require systemic immunosuppression.
  - c. Grade 3 or 4 serum electrolyte or mineral abnormalities responsive to supplementation.
  - d. Grade 3 or 4 amylase or lipase abnormalities that are not associated with diabetes mellitus (DM), associated liver or gall bladder inflammation clinical manifestations of pancreatitis and which decrease to  $\leq$  Grade 2 within 7 days.
  - e. Grade 3 rash/oral lesions that resolves to Grade  $\leq$  1 within 7 days
  - f. Fever greater than 40°C of  $\leq$  24 hr duration
  - g. Grade 3 fatigue that resolves to Grade  $\leq$  2 within 7 days
  - h. Grade 3 creatinine increased that resolves to Grade  $\leq$  1 or baseline within 7 days
  - i. Grade 3 pleural effusion that resolves per [Section 6.8](#)
- Grade 2 fever that does not resolve to Grade  $\leq$  1 within 7 days
- Grade 2 uveitis, eye pain, or blurred vision that does not respond to topical therapy and does not improve to Grade 1 prior to next scheduled dose
- Grade 2 non-hematological toxicity requiring systemic immunosuppressive therapy, including but not limited to, autoimmunity of the lung, heart, kidney, bowel, CNS, pituitary or eye, with the specific exclusion of:
  - a. Grade 2 pleural effusion that resolves per [Section 6.8](#)
  - b. Drugs will be held for grade 2 cardiac dysfunction pending evaluation.
- Grade 2 endocrine toxicity requiring hormone replacement, with the exception of Grade 2 hypothyroidism, thyroiditis and thyroid dysfunction adequately managed with thyroid hormone replacement (see [Section 6.11](#))
- Grade 2 adrenal insufficiency
- Parts A and B: Grade 2 colitis or Grade 2 diarrhea attributable to protocol therapy that persists for  $>$  7 days will be considered a DLT.

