If at least one Cycle 1 dose limiting toxicity occurs among the first 10 patients or 4 patients with dose limiting toxicities among 20 patients, then the study will close and conclude that the dose level is too toxic. This rule will provide  $\geq 89\%$  power to terminate the study in stage 1 and  $\geq 90\%$  power overall to terminate the study due to excessive Cycle 1 toxicity when the true cycle 1 toxicity is  $\geq 20\%$ . Otherwise, the study will continue per the 10+10 Simon two-stage design. The overall type 1 error rate for this rule is 40% if the true Cycle 1 toxicity is 0.05 and 66% if the true toxicity is 0.10.

All grade 3, 4, and 5 toxicity attributed to protocol therapy will reviewed weekly by the study committee and discussed during the scheduled monthly sponsor calls in order to determine the need for any changes. Consideration to open the second stage will be discussed by all approved parties (i.e. DSMC, NCI) following the release of the aggregated data for all events.

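### Table 8.1 schedules no amylase or lipase during Cycle 1, although Section 5.4.1 makes a Grade 3-4 elevation lasting over 7 days a DLT, so the Part E DLT count has a narrow but avoidable gap.

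*Combined protocol and SAP*

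**What the plan says.** - **Schedule (Section 8.1 table).** The row "Amylase, lipase, CRP" has a mark at pre-study and before subsequent cycles, and nothing in the Cycle 1 column. The row "Creatinine, ALT*, AST*, bilirubin" is weekly in Cycle 1, as are electrolytes. No footnote adds a Cycle 1 amylase or lipase test. On timing of the pre-cycle tests: "Studies may be obtained within 72 hours prior to the start of the subsequent cycle".
- **DLT definition (Section 5.4.1, the same for all parts).** The default is "Any Grade 3 or Grade 4 non-hematological toxicity attributable to protocol therapy with the specific exclusion of" a list of exceptions. Exclusion d begins "Grade 3 or 4 amylase or lipase abnormalities that are not associated with diabetes mellitus (DM" and goes on to require no liver or gall bladder inflammation, no clinical pancreatitis, and a fall to Grade 2 or less within 7 days.
- **Use of the count (Section 11.7.1).** "If at least one Cycle 1 dose limiting toxicity occurs among the first 10 patients", or 4 patients have one among 20, Part E closes as too toxic.
- **Cycle length (Section 5.1.5).** "Note that cycle length is 21 days for the first 4 cycles of Part E".
- **Gate to the next cycle (Section 5.2).** "Patients may continue on to the next cycle if Pancreatic Function is" Grade 1 or lower.

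**The concern.** Exclusion d is a rule about duration. To apply it one needs to know roughly when the elevation reached Grade 3 and to have a value about a week later. The exclusions for ALT, AST and creatinine have similar 7-day limits, and those tests are weekly in Cycle 1. Amylase and lipase have the limit without the tests. A site that follows the schedule exactly can therefore miss, or be unable to date, an event that the protocol defines as a DLT.

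This matters in Part E because one Cycle 1 DLT among the first 10 patients closes it. A single missed or disputed case can decide the outcome.

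**Working it through.** **1. When the first on-treatment value falls.** Cycle 1 lasts 21 days, so Cycle 2 starts on Day 22 if on time. The 72-hour window puts the draw at about Day 19-21.

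**2. Which cases that draw covers.**

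| Case | Covered by a scheduled test? |
|---|---|
| Grade 3-4 still present at the draw | Yes. The Section 5.2 gate, the Section 6.5 rules for Grade 3 and 4, and the DLT for a treatment delay over 7 days (Section 5.4.1) largely settle it |
| Onset of an elevation first found at the draw | No. It may already have lasted over 7 days |
| Asymptomatic, over 7 days, cleared before the draw (for example Day 4 to Day 16) | No |
| Patient leaves before Cycle 2 | No. Section 10.1 continues the Section 8.1 observations, but the Cycle 1 column contains neither assay |

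Section 11.2.1 ties DLT evaluability to Cycle 1 toxicity monitoring only for Parts A and C, so it does not close the gap in Part E.

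**3. How often a transient elevation would be over by the draw.** Assumption: onset uniform over the 20-day span from Day 1 to Day 21, one draw on Day S, Grade 3 or more for D days. The share already over is (S - D - 1)/20.

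- D = 8: 10/20 to 12/20, or 50-60%, for S = 19 to 21
- D = 10: 8/20 to 10/20, or 40-50%
- D = 14: 4/20 to 6/20, or 20-30%

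**4. The plan's own figures.** With p the Cycle 1 DLT rate:

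- Stage 1 stop = 1 - (1 - p)^10
- Overall stop = stage 1 stop + (1 - p)^10 × P(Bin(10, p) ≥ 4)

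| p | Stage 1 | Overall | Stated |
|---|---|---|---|
| 0.05 | 0.401 | 0.402 | 40% overall |
| 0.10 | 0.651 | 0.656 | 66% overall |
| 0.20 | 0.893 | 0.906 | at least 89% and at least 90% |

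All reproduce.

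**5. Effect of unseen events, true rate 20%.** Assumption: 1, 2 or 3 of the 20 percentage points are amylase/lipase DLTs that go wholly unseen. The documents give no such rate.

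| Unseen points | Detected p | Stage 1 | Overall |
|---|---|---|---|
| 0 | 0.20 | 0.893 | 0.906 |
| 1 | 0.19 | 0.878 | 0.891 |
| 2 | 0.18 | 0.863 | 0.875 |
| 3 | 0.17 | 0.845 | 0.856 |

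**6. The other direction, true rate 10%.** With 1, 2 or 3 points unseen, stage 1 closure is 1 - 0.91^10 = 0.61, 1 - 0.92^10 = 0.57 or 1 - 0.93^10 = 0.52. With all events seen it is 0.65. Better ascertainment therefore also raises closure at a rate where Section 11.7.1 counts closure as a type 1 error.

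**7. How often one event decides stage 1.** P(exactly one DLT in 10) = 10p(1 - p)^9 = 0.315, 0.387 and 0.268 at p = 0.05, 0.10 and 0.20.

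**The case against.** The strongest reply is that the existing rules leave only a small remainder. A Grade 3-4 lipase at the pre-Cycle 2 draw must be re-tested before Cycle 2 can start, because the gate is Grade 1, stricter than the Grade 2 in exclusion d. If treatment is delayed more than 7 days, the delay is itself a DLT. Symptomatic patients would probably be tested on clinical grounds: history and examination are weekly in Cycle 1, and Section 7.3 tells sites to consider pancreatitis. Section 6.5 describes asymptomatic lipase elevation as usually self-limited, which could explain a lighter schedule. This stands, and it confines the point to the three uncovered cases.

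Weekly draws would not give an exact onset date either, so ALT, AST and creatinine share some of the ambiguity. That also stands, but the difference is material. With draws at most 7 days apart, an elevation lasting longer than 7 days within the sampled period is present at one of them.

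A reader might infer from the nivolumab risk list in Section 9.1.9 that up to 20% of patients would have such a DLT. The list does not support that. Its band (20% or less) is not limited by grade, duration or cycle, and the ipilimumab list in Section 9.2.8 puts lipase and amylase increases among events with insufficient evidence of causation.

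**Conclusion.** The point holds in a limited form. The Cycle 1 schedule in Table 8.1 does not support the 7-day criterion in exclusion d, and the Part E closing rule depends on that criterion being applied. The gap is an asymptomatic elevation of more than 7 days that clears before about Day 19, the unknown onset of one first found at the draw, and patients who leave before Cycle 2.

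A reader might infer that the stated 89% and 90% power are wrong, or that Part E is shown to have a power deficit. Neither follows. The figures are correct for the true DLT rate under complete ascertainment, and the loss of 1.5 percentage points in stage 1 stopping per the first unseen point (0.893 to 0.878) rests on an assumed rate. Nor are elevations at the end of the cycle generally unclassifiable, since most are settled by rules already in the protocol. The case for a change rests on the mismatch between the two sections and the low cost of removing it.

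**What to change.** Reconcile Table 8.1 with Section 5.4.1:

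- Enter amylase and lipase as weekly in the Cycle 1 column, drawn with the existing weekly chemistry.
- Add a footnote requiring a repeat value after a Grade 3-4 result, timed so that exclusion d can be applied before the Cycle 1 DLT count is closed. Footnote 2 already does the equivalent for Grade 4 neutropenia, with repeat counts until recovery or until the DLT criteria are met.
- State how an elevation of unknown onset, first found at the pre-Cycle 2 draw, is classified.

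DLT thresholds and treatment rules stay as written.

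The cost is one table cell, a footnote, and two assays on blood already drawn each week, plus any repeat. More qualifying events would be counted, as Section 5.4.1 already requires. That raises the chance of closing Part E at low true rates, up to the stated 40% at 5% and 66% at 10%.
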